### ***Sample procedures***

The study will be conducted in the regions of Oromia and Amhara. 70 kebeles across 13 Woredas will be purposively sampled according to prior SPIR activities. In particular, sampled kebeles will be those that 1) previously received enhanced nutrition interventions under the SPIR I either through Community Health facilitators or Men’s Group Facilitators and thus have trained staff, 2) are not immediately adjacent to areas experiencing armed conflict, and 3) are accessible. Within each of the 70 selected kebeles, up to six villages with at least 10 PSNP households will be eligible to participate and chosen randomly. Most kebeles have between 3-5 villages with at least 10 PSNP households. In these cases, all villages within the kebele will be included in the study. In the rare cases where there are more than 6 villages per kebele, the largest 6 villages will be chosen to be included in the study.

In each village, up to 50 PSNP households will be screened for eligibility into the study. In villages with less than 50 PSNP households, all households will be screened. For villages with more than 50 PSNP households, households will be randomly ordered and the first 50 will be selected for screening. Through the screening survey, up to eight men and eight women per village who meet the inclusion criteria (the three criteria are: 1) are between 18-59 years old, 2) shows signs of depression or dysfunction as described below, 3) are the main decisionmaker or spouse) will be included in the study.

### **Data Collection**

Laterite will lead the fieldwork for data collection in close cooperation with the IFPRI evaluation team. Laterite is a data, research, and technical advisory firm specializing in data collection and development research projects in East Africa. The data collection will consist of a short screening survey in study villages (June 2022), followed by a baseline survey a few weeks later (July-August

---

 Villages with less than 10 PSNP households were dropped as they would likely not have enough eligible participants to form a gPM+ group.

 We only keep a maximum of 6 villages, due to logistical constraints in implementing the gPM+ intervention. We keep the largest 6 villages, because we expect only a fraction of PSNP households to exhibit signs of depressive and be eligible for the study.

 We expect about 30% of households screened to be eligible to participate in the study. Given that we were aiming for groups of 8 men and 8 women to participate in gPM+, we expected that 50 households for the screening would be sufficient to reach this maximum group size.

2022) for individuals screened into the study. Following the intervention, two endline surveys will be conducted. The first will occur right after the intervention is completed (Sept-Oct 2022), and the second will be a 1-year post-intervention (Sept-Oct 2023).

### ***Screening Survey***

The screening survey will be conducted on PSNP clients in each study village to assess whether individuals are eligible to be included in the study. Per household, up to two people aged 18-59 years will be screened (the primary decision-maker and spouse). The screening survey will assess depression and functionality using the Patient Health Questionnaire (PHQ-9) and the WHO Disability Assessment Schedule 2.0 (WHODAS). We plan to use a cutoff of 5 for the PHQ-9 and 17 for the WHODAS. The PHQ-9 has been validated in Ethiopia, and a cutoff of 5 has been identified as optimal for identifying possible depressive disorders in primary care settings in Ethiopia (Hanlon et al. 2015; Keynejad et al. 2020; Bitew et al. 2021).

Although not all villages in the study will be assigned to gPM+, the screening assessment will occur in all villages to ensure that the sample selection criteria are similar across villages. All individuals that are screened into the study will receive information on locally available mental health services and be informed that they may be contacted again in a few days to conduct the longer baseline interview. In contrast, those with severe forms of depression (a PHQ-9 score of 20 or above) or those having suicidal attempts or ideations, assessed by the safety protocol, will be referred to health facilities with psychosocial support services under supervision by a focal person and will not be included in the study.

### ***Baseline and end-line surveys***

The baseline and endline questionnaires will be questionnaires of approximately 1:30 hours. The questionnaires will be conducted using Computer Assisted Personalized Interviews (CAPI) on tablets with SurveyCTO software. The questionnaires will be translated into Amharic and Afan Oromo, and interviews will be conducted in these two languages. The surveys will be composed of two parts. The first part will comprise household-level modules such as household roster, housing, assets, consumption, food security, investments, and occurrence of shocking events. The second part will be composed of individual-level modules administered to the individuals screened for the study. These modules include instruments for measuring depression, stress, anxiety, coping, self-efficacy, time and risk preference, savings, intimate partner violence, time use, and childcare.

At baseline, we will collect basic demographic information. At endline, we will ask about participants' experience with the gPM+ therapy and at 1 year post endline, their experience with the lump-sum cash transfer.

## Estimation

### *Primary and secondary outcomes*

The study's primary outcomes are those related to mental health, economic standing, and daily activities and childcare (Table 2). The mental health-related outcomes include depressive symptoms as measured by the PHQ-9, stress as measured by the Perceived Stress Scale (PSS-10), post-traumatic stress as measured by the PCL-C, anxiety as measured by the General Anxiety Disorder 7 (GAD-7-), and functional impairment as measured by the WHO Disability Assessment Schedule 2.0 (WHODAS 2.0). The economic outcomes include the total value of productive assets; total value of per capita consumption expenditures, food insecurity, and savings. Lastly, we are interested in how improved mental health leads to improved time-use and care activities. Thus our third set of outcomes include time-use with respect to non-economic activities, income-generating activities, other activities, and childcare and discipline. Given that some outcomes may take more time to change and the cash transfer was rolled out after the endline, some outcomes (mainly the economic outcomes) will be analyzed only at 1 year-post endline.

For all primary outcomes we will create raw scores and standardized scores. Results on raw scores will be reported in the appendices. We will also create summary indices at the domain level following Kling et al. 2007.

**Table 2: Primary outcomes**

Domain	Indicators	Endline	1-year post endline
Mental health	PHQ-9 – a measure of depressive symptoms – total score from 9 questions converted to standardized unit using control mean and SD	X	X
	Perceived stress scale (PSS-10) – total score from 10 questions converted to standardized unit using control mean and SD	X	X
	Post-traumatic stress, PCL-C – total score from 6 questions converted to standardized unit using control mean and SD	X	X

	General Anxiety Disorder 7 (GAD-7-) – total score from 7 questions converted to standardized unit using control mean and SD	X	X
	WHO Disability Assessment Schedule 2.0 (WHODAS 2.0) – total score from 12 questions converted to standardized unit using control mean and SD	X	X
Economic	The total value of productive assets- total value transformed using inverse-hyperbolic sine transformation and then standardized using control mean and SD		X
	Total value of monthly per capita expenditures – total value of food and non-food consumption transformed using inverse-hyperbolic sine transformation and then standardized using control mean and SD		X
	Food insecurity experience scale- total score converted to standardized unit using control mean and SD		X
	Savings- binary indicator that equals one if individual deposited any money in the last 12 months in any type of savings account, converted to standardized unit using control mean and SD		X
Activity and childcare	Non-economic activities: total hours spent in non-economic activities in the last 24 hours, converted to standardized unit using control mean and SD	X	X
	Income generating activities: total hours spent in income generating activities in the last week, converted to standardized unit using control mean and SD	X	X
	Other activities: summation of number of other activities participated, converted to standardized unit using control mean and SD	X	X
	Childcare – total number of activities, converted to standardized unit using control mean and SD	X	X
	Child discipline: total score, converted to standardized unit using control mean and SD	X	X
	Child neglect : total score, converted to standardized unit using control mean and SD	X	X

In addition, to the primary outcomes of interest, we are interested in potential pathways through which the gPM+ and cash could improve mental health and economic outcomes. These secondary outcomes include improvements in an individual's coping skills (as measured by an abbreviated Brief Cope, Tension reduction, alcohol and khat consumption, and social support), psychosocial skills (as measured by general self-efficacy); intrahousehold relationships (as measured by the WHO Violence Against Women Instrument for IPV), and economic preferences such as time and risk (as measured by the Global Preference survey) and subsequent investments. These outcomes are listed in Table 3.

**Table 3: Secondary outcomes**

Domain	Measure
Coping mechanisms	Alcohol and Khat consumption
	Tension reduction
	Brief Cope (shortened to 6 items) – instrument to measure coping with stressful life events
	Multi-dimensional Scale of Perceived Social Support (MSPSS)
Psychosocial skills	General self-efficacy
Preferences	Time preference (Global preference survey)
	Risk preference (Global preference survey)
	Value of Investments in last 12 months
Intrahousehold relationships	Intimate Partner Violence (WHO violence against women instrument)

### ***Empirical approach***

Impacts will be measured immediately following the intervention (endline) and 1-year post-program. We will estimate intent-to-treat (ITT) effects following the assigned treatment using the ANCOVA model when baseline outcome variables are available. We will run probit models for binary outcomes and ordinary least squares models for continuous variables.

*R1: What is the immediate impact of gPM+ on mental health and daily activity?*

To answer the first research question, we will rely on the baseline and endline data. Given that the cash transfer has not yet been distributed, we will combine arms 1 and 3 (no gPM+) and arms 2 and 4 (gPM+) to estimate the following equation:

$$Y_{ihvk}^1 = \beta_0 + \beta_1 gPM_{vk} + \beta_2 X_{ihvk}^0 + \beta_3 Y_{ihvk}^0 + \mu_k + \varepsilon_{ihvk} \quad (\text{EQ 1})$$

Where  $Y_{ihvk}^1$  is the outcome of interest at endline for individual  $i$  from household  $h$  from village  $v$  in kebele  $k$ ; and  $Y_{ihvk}^0$  is the outcome of interest at baseline.  $gPM_{vk}$  is an indicator that equals one if village,  $v$ , was randomized to the gPM+ treatment.  $X_{ihvk}^0$  is a vector of baseline control variables that will include age and sex of the respondent for individual level outcomes. As a robustness check other possible baseline control variables will be included such as enumerator sex and the number and age of children (for childcare outcomes). The specification also includes kebele fixed effects,  $\mu_k$ . Standard errors will be clustered at the village level. We will assess heterogeneity of impacts by sex of the study participant, region, and PHQ-9 score as measured in the screening survey.

*R2-R4: What is the impact of gPM+ on PSNP clients' mental health, daily activity, and economic well-being 1-year after gPM+ sessions end? What is the impact of a one-time lump-sum cash transfer on mental health, daily activity, and economic well-being 1-year after gPM+ sessions end?; What is the added impact of combining gPM+ with a one-time lump sum cash transfer one year after gPM+ sessions end?*

To answer research questions 2-4, we will rely on the baseline and 1-year post-endline data. The main specification we will estimate is the following:

$$Y_{ihvkw}^2 = \beta_0 + \beta_1 Cash_{kw} + \beta_2 gPM_{vkw} + \beta_3 Cash_{kw} * gPM_{vkw} + \beta_4 X_{ihvkw}^0 + \beta_5 Y_{ihvkw}^0 + \gamma_w + \varepsilon_{ihvkw} \quad (\text{EQ 2})$$

Where  $Y_{ihvkw}^2$  is the outcome of interest at 1-year post-endline for individual  $i$  from household  $h$  from village  $v$  in kebele  $k$  and woreda  $w$ ; and  $Y_{ihvkw}^0$  is the outcome of interest at baseline.  $Cash_{kw}$  is an indicator that equals one if kebele,  $k$ , was randomized to the one-time lump-sum cash treatment;  $gPM_{vkw}$  is an indicator that equals one if village,  $v$ , was randomized to the gPM+ treatment.  $X_{ihvkw}^0$  is a vector of baseline control variables that will include age and sex of the respondent for individual level outcomes. The specification also includes woreda fixed effects,  $\gamma_w$ . As a robustness check we will also run a specification with kebele fixed effects and other possible baseline control variables will be included such as enumerator sex and the number and age of children (for childcare outcomes). Standard errors will be clustered at the village level. We will

assess heterogeneity of impacts by sex of the study participant, region, and PHQ-9 score measured in the screening survey.

In this model,  $\beta_1$  measure the impact of the cash treatment compared to the control group 1-year after the gPM+ sessions ended;  $\beta_2$  the impact of the gPM+ treatment compared to the control group 1-year after the gPM+ sessions ended; and  $\beta_3$  represents the added impact of combining the cash and gPM+ treatment.

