## **Sample and power calculations**

### ***Power calculations***

Power calculations for this study focused on a primary mental health outcome, PHQ-9, and economic outcome, the total value of productive assets. PHQ-9 is a widely used depression diagnostic instrument with scores that range from 0-27. For both outcomes, we drew on data from the endline SPIR I impact evaluation conducted in the same regions of Oromia and Amhara. Given

that SPIR I data did not have data on daily activities, we did not conduct power calculations on this outcome.

We power the study for estimating impacts 1-year after the gPM+ sessions ended across the 4 intervention groups as this requires the largest sample. Power calculations considered the study's design, adjusting for clustering and autocorrelation. Autocorrelations were estimated using the SPIR endline and midline data, while intra-cluster correlations (ICC) were assessed at the kebele level. Power calculations were conducted in STATA using `clustersampsi` command. The desired statistical power was set at 80%, and the desired significance level was set to 0.05. Given that the number of kebeles, villages, and gPM+ group size were pre-determined, we calculate the minimal detectable effect at 1 year post gPM+ for a given number of clusters and cluster size.

We set the number of villages to 252. The number of individuals per village will depend on the number of individuals screened into the study. The max gPM+ group size is 8 women and 8 men per village and the minimum is 3 women and 3 men. On average we expect about 12 individuals per village (6 men and 6 women) at baseline with a coefficient of variation of 0.25. Assuming 8% attrition, rounded to the nearest whole number, the number of individuals per village at 1 year post endline is 11, for a total of 2,772 individuals. For household level economic outcomes, the number of households is estimated differently as two individuals per household (main decision-maker and spouse) are eligible to participate in the study. We expect about 18 percent of the sample to be husband/wife pairs from the same household. This will reduce the number of observations for household-level economic outcomes to 2,218 households.

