These parameters give us a minimal detectable effect (MDE) of 0.22 standard deviations on the PHQ-9 score and 0.25 standard deviations on the value of productive assets (Table 1), both which are considered small effect sizes. The MDE for the PHQ-9 is a lower bound effect size comparable to those found in Nepal and Pakistan (0.2-0.38 mean standardized difference for PHQ-9) 3-months after the gPM+ intervention (Jordans et al. 2021; Rahman et al. 2019).

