**Table 1: Minimal detectable effect for given sample at 1-year post-program data collection**

	MDE (SD)	ICC	Corr	K villages, per arm	N per cluster	N per arm	Total sample at 1 year post program
PHQ-9 score	0.22	0.13	0.29	63	11	693	2,772
Value of productive	0.25	0.16	0.23	63	9	567	2,268

assets							
--------	--	--	--	--	--	--	--

\*2nd stage comparison of villages across the four different treatment arms

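### The main models in EQ 1 and EQ 2 leave out the screening PHQ-9 and WHODAS, which are already held for every participant; adding them is a free but minor gain in precision.

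*Combined protocol and SAP*

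**What the plan says.** Under Empirical approach, both equations contain the treatment terms, X, the baseline value of the outcome when there is one, and fixed effects (kebele in EQ 1, woreda in EQ 2). X "is a vector of baseline control variables that will include age and sex of the respondent for individual level outcomes". Further baseline covariates come in only as a robustness check. That list is open-ended, and its examples are enumerator sex and the number and age of children.

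The Screening Survey section says "The screening survey will assess depression and functionality using the Patient Health Questionnaire (PHQ-9) and the WHO Disability Assessment Schedule 2.0 (WHODAS"). Screening takes place in all study villages in June 2022, before baseline and before any intervention, and both scores feed the eligibility decision. In the estimation section the only use of either is heterogeneity by "PHQ-9 score as measured in the screening survey". Screening WHODAS has no role there.

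Table 2 makes PHQ-9 and WHODAS 2.0 primary outcomes at endline and at one year. The individual modules listed under Baseline and end-line surveys name depression, stress and anxiety, among others. They do not name functional impairment or WHODAS, though the list is worded as examples and may be incomplete.

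**The concern.** A single PHQ-9 score is a noisy reading of a person's underlying level; the plan's own autocorrelation is 0.29. A second pre-treatment reading on the same person may therefore carry prognostic information that the baseline score misses. Adjusting for it would narrow the confidence interval at no field cost and would remove chance imbalance between arms on the variables that determined entry.

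For WHODAS the stake may be larger. The plan uses ANCOVA only where a baseline outcome exists. If WHODAS was measured at screening but not repeated at baseline, the models as written have no lagged value for that primary outcome, although a pre-treatment value is on file.

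**Working it through.** **Inputs from the plan.** "The desired statistical power was set at 80%, and the desired significance level was set to 0.05" (taken as two-sided). Table 1 row: "PHQ-9 score 0.22 0.13 0.29 63 11 693 2,772", that is MDE, ICC, correlation, villages per arm, participants per village, participants per arm and total. Power calculations also sets the CV of cluster size at 0.25. On losses to follow-up it says: "Assuming 8% attrition, rounded to the nearest whole number, the number of individuals per village at 1 year post endline is 11".

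**Assumed, because the documents give no value.** s, the correlation of screening score with outcome, and ρ, the correlation of screening score with baseline score.

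**Step 1: reproduce the plan's figure.** MDE = (1.960 + 0.842) × √[2 × DE × (1 − r²) / (K × m)].
- DE = 1 + [(1 + 0.25²) × 11 − 1] × 0.13 = 2.389.
- 1 − r² = 1 − 0.29² = 0.9159, and K × m = 63 × 11 = 693.
- MDE = 2.802 × √(2 × 2.389 × 0.9159 / 693) = 0.2226. With equal cluster sizes it is 0.2184; t-based variants give 0.2202 and 0.2244.

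This agrees with the plan: "These parameters give us a minimal detectable effect (MDE) of 0.22 standard deviations on the PHQ-9 score". The figure credits one prior measure only, so planned power does not rely on the screening scores.

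**Step 2: add screening PHQ-9 at one year.** Replace r² by R² = (r² + s² − 2rsρ) / (1 − ρ²). If screening is as predictive as baseline (s = r = 0.29), this is 2r² / (1 + ρ) = 0.1682 / (1 + ρ).

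| ρ (assumed) | R² | Residual variance ratio | SE falls | MDE | Power at 0.22 SD |
|---|---|---|---|---|---|
| none added | 0.0841 | 1 | – | 0.2226 | 79.1% |
| 0.4 | 0.1201 | 0.9606 | 2.0% | 0.2182 | 80.6% |
| 0.6 | 0.1051 | 0.9770 | 1.1% | 0.2201 | 80.0% |
| 0.8 | 0.0934 | 0.9898 | 0.5% | 0.2215 | 79.5% |

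In this formula the three gains equal about 114, 65 and 29 extra participants on 2,772.

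**Step 3: vary s** (ρ = 0.4 / 0.6 / 0.8).
- s = 0.25: the SE falls 1.2% / 0.5% / 0.05%.
- s = 0.35: it falls 3.6% / 2.7% / 2.1%.
- s = r × ρ (screening predicts only through baseline): no gain.

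Adding screening WHODAS as well, with s = 0.29, an assumed WHODAS-outcome correlation of 0.10-0.25, WHODAS-PHQ-9 correlation of 0.3-0.5 and ρ of 0.5-0.8, gives a total SE reduction of about 0.5 to 2.7%.

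**Step 4: endline (EQ 1).** The gap is about two months, so correlations may be higher. At an assumed r = s = 0.5 and ρ = 0.6, R² rises from 0.25 to 0.3125, and the SE falls by 1 − √(0.6875 / 0.75) = 4.3%. That ignores selection on the screening score. A simulation restricted to screening PHQ-9 of 5-19 or the top 12% of WHODAS (skewed PHQ-9 with 26% at 5 or more and 5.5% at 10 or more; correlations 0.4-0.7) cuts residual variance by 3 to 8% at endline and 1.4 to 2.4% at one year. In SE terms:
- Endline: 1 − √0.97 = 1.5% to 1 − √0.92 = 4.1%.
- One year: 1 − √0.986 = 0.7% to 1 − √0.976 = 1.2%.

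**Step 5: WHODAS, if there is no baseline value.** Using screening WHODAS as the lagged outcome cuts the SE by 1 − √(1 − r²): 2.0%, 4.3% and 8.3% at assumed r = 0.20, 0.29 and 0.40.

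**The case against.** The models are already ANCOVA with fixed effects, their estimates are valid without the extra scores, and the stated 0.22 SD reproduces without them. After the change the MDE still rounds to 0.22. All of this stands.

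The larger relative gain also comes where it is needed least. EQ 1 pools arms, about 126 villages against 126, so on Table 1 inputs its MDE is about 0.2226 / √2 = 0.157. That is already below the 0.2-0.38 range the plan cites from earlier trials.

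Clustering may shrink the one-year gain further. With ICC 0.13 and 11 per village, the shared part of an arm mean's variance is 1.43 / 2.30, about 62%, before fixed effects. If a second score averages out only individual noise, the R² increments of 0.036 and 0.0093 in Step 2 (ρ = 0.4 and 0.8) save 1 − √(1 − 0.036 / (2.30 × 0.9159)) = 0.9% and, in the same way, 0.2% of SE. The 0.5 to 2% range assumes the gain applies to both components.

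A reader might infer several stronger things, which the documents do not support:
- That the models adjust for nothing beyond age, sex and one score. They also carry fixed effects, and the robustness list is open.
- That endline residual variance would fall by 8 to 14%. That comes from the two-score formula at a common correlation of 0.4-0.6, which ignores the eligibility cut-offs (PHQ-9 of 5, WHODAS of 17, exclusion at PHQ-9 of 20 or above).
- That WHODAS is known to be repeated, or known to be absent, at baseline. The module list settles neither.

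Finally, the plan is dated October 10, 2022, inside the planned September-October 2022 endline window. A late change to the main specification therefore has some pre-specification cost.

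**Conclusion.** The point holds as a minor efficiency suggestion. Two pre-treatment scores that every participant should have are left out of the main specification for the very outcomes they measure. No error, bias or power shortfall follows from that. A reader should not take the 79.1% at 0.22 SD as a shortfall either; it reflects rounding of an MDE that reproduces as 0.218 to 0.224 across variants.

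The size rests on assumed correlations: about 0.5 to 2% of SE at one year if screening is as predictive as baseline, about 1.5 to 4% at endline after allowing for selection, and possibly nothing. The more useful part is conditional. If WHODAS was not collected at baseline, the screening value would restore ANCOVA for that primary outcome, worth about 2 to 8% of SE at correlations of 0.20 to 0.40.

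**What to change.** In EQ 1 and EQ 2, add screening PHQ-9 and screening WHODAS to X in the main specification for the PHQ-9 and WHODAS outcomes, and optionally for all mental-health outcomes, alongside the baseline outcome. State whether WHODAS is in the baseline survey; if it is not, say that the screening WHODAS serves as the lagged outcome.

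The cost is a sentence or two of SAP text. The data are collected already, and each score uses about one degree of freedom. Because of the plan's date, record the change with a date before any outcome data are analysed. If that is no longer possible, name the adjusted model as a robustness check.

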**Figure 1: Study design**

### ***Study population***

The population for this study are individuals residing in Amhara and Oromia and registered and assisted by PSNP public works program. Moreover, to be eligible, individuals must have signs and symptoms of depression or dysfunction, be between 18 and 59 years old, and be the main decision-maker or spouse of the main decisionmaker. The last criterion is added because we are interested in the relationship between mental health and economic decision-making, which is more relevant for the main household decision-makers. We allow both the primary decision-maker and spouse to be eligible because depression across spouses is often correlated, and therapy may be more beneficial when both are treated. Individuals will be excluded from the study if they present evidence of severe depression or suicide. A quick screening exercise will be conducted in the selected villages to identify eligible participants. The screening exercise will be based on the PSNP client list and include a brief survey that screens individuals for inclusion in the study (see section on “Screening survey” for more detail).

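### Three child outcomes that can apply only to participants with a child share an index with activities everyone has, and the number and age of children are left to a robustness check

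*Combined protocol and SAP*

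**What the plan says.** Table 2 lists six primary indicators in the domain of activity and childcare, all measured at endline and at one year. Three are non-economic hours, income-generating hours and a count of other activities. The other three concern children:

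- "Childcare – total number of activities, converted to standardized unit using control mean and SD"
- "Child discipline: total score, converted to standardized unit using control mean and SD"
- "Child neglect : total score, converted to standardized unit using control mean and SD"

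No denominator is given for any of the six. The section on primary and secondary outcomes treats them as one group: "our third set of outcomes include time-use with respect to non-economic activities, income-generating activities, other activities, and childcare and discipline". The same section adds a summary index for each domain, by a method that is cited but not described. The cited source is not in the reference list.

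On eligibility, Study population requires that a person "be between 18 and 59 years old, and be the main decision-maker or spouse of the main decisionmaker", together with signs of depression or dysfunction. Sample procedures repeats this, ending with "3) are the main decisionmaker or spouse". Neither mentions a child.

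In Empirical approach, the main covariates of EQ 1 and EQ 2 are the respondent's age and sex, the baseline outcome where available, and fixed effects. A robustness check adds "enumerator sex and the number and age of children (for childcare outcomes". The same arrangement is stated for EQ 2.

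**The concern.** A childcare count, a discipline score and a neglect score can be meaningful only for someone responsible for a child. The documents do not say this outright, but it follows from the content of the measures, and the plan itself links the number and age of children to these outcomes. Since eligibility does not require a child, some participants probably have no value on half of the domain's components.

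The research questions on daily activities concern PSNP clients in general, not only those with children. With one index per domain, the meaning of the index depends on a coding choice that the plan does not state: missing with the available items averaged, missing with the person dropped, or zero. These choices can give different results from the same data. Separately, number and age of children are likely predictors of the three child outcomes and can be derived from the household roster, yet the main models do not use them.

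**Working it through.** **Inputs from the documents.** Table 1, PHQ-9 row: ICC 0.13, correlation 0.29, k = 63 villages per arm, m = 11 per village. Power calculations: CV of cluster size 0.25, power 80%, significance level 0.05 (taken as two-sided). No ICC, correlation or power calculation is given for this domain, so the PHQ-9 values are borrowed.

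**Assumptions.** The share p of participants with a child is not given; I take 0.7 to 0.9. The extra variance explained by number and age of children is not given; I take 5 to 15%.

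**1. Reproduce the plan's figure.**

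DE = 1 + ((1 + CV²)m − 1) × ICC = 1 + (1.0625 × 11 − 1) × 0.13 = 2.389

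MDE = 2.80 × √(2 × DE × (1 − 0.29²) / (63m)) = 2.80 × √(2 × 2.389 × 0.9159 / 693) = 0.2226

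The plan states 0.22. The formula also gives 0.2493 for productive assets (m = 9, ICC 0.16, correlation 0.23), against a stated 0.25. No stated figure is in dispute.

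**2. What the index measures if available items are averaged with equal weights.** For a participant with a child, 3 of 6 items concern children; for one without, 0 of 3.

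- Effect d on the child items only: mean index effect = p × 0.5 × d, which is 0.50d at p = 1, 0.45d at p = 0.9 and 0.35d at p = 0.7.
- Effect a on the activity items only: mean index effect = (0.5p + (1 − p)) × a, which is 0.50a at p = 1, 0.55a at p = 0.9 and 0.65a at p = 0.7.

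The weight on each kind of effect therefore depends on how many participants have children.

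**3. Cost of limiting the child outcomes to participants with a child.** Replace m by 11p in step 1.

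| p | m | Analysed N (252 × m) | MDE, SD |
|---|---|---|---|
| 1.0 | 11 | 2,772 | 0.223 |
| 0.9 | 9.9 | 2,495 | 0.227 |
| 0.7 | 7.7 | 1,940 | 0.239 |

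This is the one-year contrast between arms. Endline under EQ 1 pools arms and was not computed.

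**4. Zero-coding, as one possibility only.** A 0.22 SD effect among participants with a child becomes 0.22 × 0.9 = 0.20 to 0.22 × 0.7 = 0.15 on their SD scale. The plan standardises on the control SD, and zeros widen that SD. With an assumed mean of 4 and SD of 2 among participants with a child, the pooled variance is p(2² + 4²) − (4p)². The standardised effect is then 0.9 × 0.44/√5.04 = 0.176 at p = 0.9 and 0.7 × 0.44/√6.16 = 0.124 at p = 0.7.

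**5. Precision from the child covariates.** The ratio of standard errors is √(1 − extra R²): √0.95 = 0.975 and √0.85 = 0.922, a fall of 2.5 to 8%. This is an upper limit, because the main model already adjusts for the baseline outcome where available and that may carry much of the same information.

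**The case against.** The strongest reply is that the plan is silent here rather than wrong. A reader might infer that Table 2 scores the three child outcomes for every participant, with zero for those without a child, so that effects are diluted. The documents do not support that: Table 2 gives no denominator and no rule for zeros. Tying number and age of children to these outcomes suggests, if anything, that the authors see them as dependent on having a child. The cited index method may also have its own rule for missing components, which cannot be read from the documents.

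Second, a reader might infer that leaving number and age of children out of the main models biases the treatment effects. It does not, because villages and kebeles are randomised. The adjusted analysis is also already planned as a robustness check.

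Third, the six indicators are each primary outcomes and the index is additional, so the activity and childcare questions can still be answered separately. Grouping them has a stated reason: the plan wants to know how better mental health changes time use and care.

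All three replies stand as limits on the point. They do not remove it. An index whose content differs between participants remains hard to interpret whichever missing-data rule applies, and the better specification uses data that the survey already collects.

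**Conclusion.** The point holds as a low-cost improvement, not as an error that invalidates a primary analysis. On the plan's own text, one domain index combines three measures that apply to everyone with three that can apply only to participants with a child, and the handling of those without a child is not stated. The domain index is the result most affected; the separate indicators are affected only in that the population for the three child outcomes is undefined.

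The possible gain from moving the covariates is a standard error smaller by at most 2.5 to 8%, on an assumed 5 to 15% of further residual variance explained. The loss from restricting the child outcomes is small: the MDE rises by about 2 to 7% (0.223 to between 0.227 and 0.239 SD) if 10 to 30% have no child. Both ranges rest on figures that the documents do not give, and the MDE borrows PHQ-9 inputs. The zero-coding figures show what one unstated rule would do and should not be read as the plan's result.

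**What to change.** 1. For childcare, child discipline and child neglect, move baseline number and age of children from the robustness check into the main EQ 1 and EQ 2.
2. Analyse these three outcomes in participants with a child in a stated age range on the baseline household roster. Use the same pre-treatment list in all arms and at both waves, and compute the control mean and SD within that group.
3. Replace the single domain index with two: an activity index (three indicators, all participants) and a childcare index (three indicators, the group in item 2). State the direction in which discipline and neglect are scored before averaging.

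This needs changes to the SAP wording and one more index, with no new data and no change of design. The price is one more summary test and the slightly smaller sample for the child outcomes shown above.
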